## 4.2 Exclusion Criteria

- (1) Intolerance to candesartan or lisinopril ;
- (2) SBP >200 or DBP >110 mm Hg;
- (3) Renal disease or hyperkalemia (SCr >1.99 mg/dl or K > 5.5 meq/dl);
- (4) Active medical or psychiatric problems (An active problem is one that requires medical attention and is deemed as a safety risk by the study physician, for example current cancer treatment, infections such as pneumonia, current gastrointestinal or other internal bleeding, HIV treatment, hematological disease, Parkinson's disease, multiple sclerosis)
- (5) Uncontrolled congestive heart failure [shortness of breath at rest or evidence of pulmonary edema on exam];
- (6) History of stroke in the past 3 years (self-reported clinical stroke within the past 3 years/ incidental infarcts on MRI scanning is allowed);
- (7) Inability to perform the study procedures (those with contraindications for MRI will be enrolled but will not undergo the MRI; those with history of asthma, COPD, or significant pulmonary disease will not undergo the CO2-reactivity protocol);
- (8) Women of childbearing potential
- (9) Current use of acetylcholine-esterase inhibitors or NMDA receptor antagonist (memantine) or a diagnosis of dementia self-report or care-giver report
- (10) In those who lack decision capacity, a *study surrogate* who can sign on their behalf will be required. Since we are enrolling only those with MCI, we anticipate that most participants will have decision capacity
- (11) Current use of Lithium, as most antihypertensive classes may lead to increased lithium toxic levels.

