## 6.6 Blood chemistries and blood count,

Blood chemistries including electrolytes (potassium, sodium, chloride and bicarbonate as well as calcium and blood urea nitrogen (BUN), and creatinine) will be measured at baseline and during the follow-up as part of the safety monitoring for hyperkalemia and renal insufficiency, as shown in Table 2. A complete blood count will also be collected at baseline and 6, and 12 months. Blood will be drawn after application of a tourniquet, by use of a small gauge needle, from an ante-cubital vein, and by an appropriately trained professional from subjects. These are part of assessing safety of the study drug and will be performed at the local Emory Clinical Laboratory.

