## 7.2 Description of Evaluations

7.2.1 Screening: Initial eligibility will be determined via phone interview.. This screening process will determine the specific inclusion and exclusion criteria that can be evaluated by self-report, including age, hypertension or blood pressure diagnosis, and prior medical issues detailed in the inclusion/exclusion criteria. Data collected during this interview will be stored de-identified for future data analysis with no links to the patient or their PHI. A study ID number will be used to collect data and will not be linked to the participant. Those who are eligible via phone interview will be invited for a clinic screening visit along with their next-of-kin, if possible. The screening visit will include: explaining study details and obtaining informed consent, cognitive assessment, medical history, current medications, 2 seated blood pressure measurements, and baseline metabolic panel. Eligible participants currently receiving antihypertensive medications who agree to stop antihypertensive medications will be instructed on a taper protocol and asked to return for baseline evaluation and randomization.

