**7.2.3 Enrollment, Baseline, and Randomization:** During this phase, blood pressure measurements, detailed neuropsychological assessments, physical exam, brain MRI, and carotid ultrasound will be completed. Blood samples will also be collected for APOE, inflammatory and endothelial markers. Randomization and study intervention will occur after baseline data collection. Participants will then be started on the study medications. For all study related testing, the test results will not be disclosed to you unless deemed necessary by the study Physician.

**7.2.4 Follow-up Visits:** Following randomization, participants will be seen every two weeks, where antihypertensive study medications will be increased until they achieve blood pressure control (<140/90 mmHg), according to the designated trial protocol for blood pressure control. Blood pressure, heart rate, weight, adverse events (AE) and serious adverse events (SAE), pill count (to assess compliance), and use of non-study medications data will be collected. Once hypertension control is achieved, participants will be seen at 3, 6 and 12 months visits. Repeat neuropsychological assessment, blood draws (EPC and inflammatory markers), and urine collection will be conducted at the 6 and 12 months visit. Repeat neuroimaging and vascular ultrasound will be repeated at 12 months. BMP will also be checked at 2 weeks after randomization if only step one is needed, 4 weeks post randomization if treatment beyond step 1 is needed, and at 3, 6 and 12 months as shown in **Table 2**. Participants will also be contacted by phone as described in Table 2, Monthly during the follow-up phase. During these phone calls, participants will be asked about missing any doses in their medications and screened for any potential adverse events.

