clinical practice. Possible side effects include: dizziness, cough (lisinopril), weakness, fatigue, lower extremity edema and constipation (amlodipine), and hypotension. Renal failure and hyperkalemia are also potential complications of candesartan and lisinopril. HCTZ may cause renal failure, volume depletion, and hypokalemia. Lisinopril may cause a dry cough and angioedema. Beta blockers may be associated with weakness and bradycardia. Adverse events will be queried at each visit. Alternatives to antihypertensive medications include no therapy, which is not safe or ethical in patients with hypertension. Drug-drug interaction will be assessed by the study physician. If there is contraindication to use the candesartan or lisinopril and one of the other participant's medications then he/she will not be able to enroll in the study. If the contraindication is between an add-on agent (amlodipine, metoprolol, or HCTZ) then the participant will be enrolled but we will avoid using that agent as an add-on as described in section 5.3. Use of lithium is a contraindication for both lisinopril and candesartan and hence lithium users are excluded. The following combinations of medications are contraindicated for the add-on drugs: Simvastatin >20 mg with amlodipine, reserpine with metoprolol, and clonidine with metoprolol.

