## **9. INTERVENTION DISCONTINUATION**

A subject may choose to withdraw from the study for any reason. The investigators may also request that the subject withdraw from the study, for safety or other reasons. Withdrawn participants will continue to be monitored by the study personnel for 2 months after the event if possible and invited to complete the final visit evaluation. The criteria for discontinuing a subject's participation include:

- (1) the subject's request,

- (2) serious adverse events that requires un-blinding,
- (3) new stroke, transient ischemic attack, or myocardial infarction that limits ability to complete the study
- (4) Symptomatic dysrhythmia
- (4) anaphylaxis or allergic reaction to study medications,
- (5) disturbing and persistent cough ( transient mild cough is not a discontinuation criterion unless participant requested it),
- (6) inability to participate due to relocation or other personal reasons,
- (7) renal failure (increase in serum Creatinine above 2.5 mg/dl) or hyperkalemia (greater than 5.8 meq)

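### The potassium limits are not printed in a usable unit, and the plan does not settle whether chemistry is measured between drug withdrawal and the first dose

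*Combined protocol and SAP*

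**What the plan says.** **Limits.** Section 4.2, exclusion (3): "Renal disease or hyperkalemia (SCr >1.99 mg/dl or K > 5.5 meq/dl". Section 9, criterion (7), discontinues for serum creatinine above 2.5 mg/dl or "hyperkalemia (greater than 5.8 meq", with no volume after the unit.

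**Timing of chemistry before study drug.**
- Section 6.6: electrolytes, BUN and creatinine "will be measured at baseline and during the follow-up as part of the safety monitoring for hyperkalemia and renal insufficiency", with a pointer to Table 2.
- Section 8.2: renal function and potassium at baseline and at months 1, 3, 6 and 12.
- Section 7.2.1: the screening visit includes "current medications, 2 seated blood pressure measurements, and baseline metabolic panel". Eligible participants on treatment who agree to stop it then "will be instructed on a taper protocol and asked to return for baseline evaluation and randomization".
- Section 7.2.3, on the baseline visit: "Blood samples will also be collected for APOE, inflammatory and endothelial markers". No chemistry is named.
- Table 2: BMP is marked in the screening block, at titration, and at 3, 6 and 12 months. Its Baseline cell is empty. CBC is marked at Baseline, 6 and 12 months.

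**State at the baseline visit.** Section 8.3 places that visit after all antihypertensives have been stopped. The study visit windows allow no more than one week off treatment.

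**The concern.** Exclusion (3) is meant to keep people with raised potassium or renal disease off the study drugs. Section 8.1 explains why that matters: "Renal failure and hyperkalemia are also potential complications of candesartan and lisinopril. HCTZ may cause renal failure, volume depletion, and hypokalemia". A limit in an unworkable unit does not do this job as written.

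The timing question follows from the same sentence. Section 8.1 says that drugs a participant may be taking at screening can themselves affect potassium or renal function. Table 3 lists prior ACEI/ARB use as a covariate, so such participants are expected. If the only pre-treatment panel is the one drawn before the taper, it describes the former regimen and not the state in which study drug starts. If a second panel is intended at the baseline visit, the schedule that sites work from omits it. Either way, the text does not tell a site which result decides eligibility.

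**Working it through.** **1. Unit.** One litre is 10 dl, so a value in meq/dl is multiplied by 10 to give meq/L.
- Exclusion limit as printed: 5.5 meq/dl × 10 = 55 meq/L.
- The stopping limit has no denominator. Read per litre it is 5.8 meq/L, and the entry limit as printed would be 55 / 5.8 = 9.48 times as high. Read per decilitre it is 5.8 × 10 = 58 meq/L. Only if both limits are read per litre do they form a workable pair.
- Creatinine is in mg/dl in both places (1.99 and 2.5), so the fault is confined to potassium.

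**2. What baseline means for chemistry.** There are two readings.
- *Reading A: it means the screening panel.* Section 7.2.1 itself calls that panel baseline, and the empty Table 2 cell and the list in 7.2.3 agree. On this reading no value exists between withdrawal and the first dose for tapered participants.
- *Reading B: it means the baseline visit.* Section 6.6 schedules the CBC at baseline, 6 and 12 months, and Table 2 marks CBC in exactly those columns. In that paragraph, then, baseline corresponds to the Baseline column for CBC. If the same holds for chemistry, Table 2 and 7.2.3 leave out a promised safety test.

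Neither reading makes all five places agree. Section 8.2 also gives a 1-month test, where 7.2.4 and the Table 2 footnote give 2 or 4 weeks depending on the titration step.

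**3. Age of a pre-taper sample under reading A.** Inputs: the taper table in 8.3 and the BMP timing in 7.2.4. Assumptions: the panel is drawn on day 0 of the taper, and randomization falls on the day of the baseline visit.
- One prior drug: baseline visit on days 8–14. Three prior drugs: days 22–28. The panel is therefore 8 to 28 days old, about 1 to 4 weeks.
- The next BMP comes 14 or 28 days after randomization. The interval between consecutive panels would run from 8 + 14 = 22 days to 28 + 28 = 56 days, about 3 to 8 weeks, covering both the withdrawal and the start of study drug.

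**4. Who is affected.** Inclusion (2) in section 4.1 also admits people on measured blood pressure alone. They have no taper, so step 3 does not apply to them. The unit error applies to everyone.

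**5. What cannot be computed.** The documents do not say how far potassium or creatinine moves after withdrawal, or how many participants sit near a limit.

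**The case against.** **The unit is a misprint that no site would follow.** The exclusion names hyperkalemia in words, and 5.5 sits naturally beside the 5.8 in section 9. This is very likely right, and no operational effect is shown. It is still an eligibility threshold that is wrong as written, with a paired limit that has no volume unit.

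**The documents do promise baseline chemistry.** Sections 6.6 and 8.2 say so, and the list in 7.2.3 is not exhaustive, since it also leaves out the CBC that Table 2 marks at that visit. This stands in part. A reader might infer that chemistry after withdrawal is definitely absent and that eligibility is decided only on the former regimen. The documents do not settle that; they show a conflict.

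**A panel on prior drugs is not uninformative.** In someone already taking an ACEI or ARB, it reflects the drug classes being started. This is fair, and it limits how much is lost in that group.

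**There are later safeguards.** A BMP follows at 2 or 4 weeks, and 8.2 allows extra testing when needed. This mitigates, but it comes after exposure and does not inform entry.

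**Stronger inferences that fail.** A reader might go on to conclude that between-arm chemistry comparisons are compromised. The section 9 limits are absolute and need no reference sample. Section 10.5 compares numbers of AEs, SAEs and incident dementia, and plans no change-from-baseline chemistry analysis. Prior-drug effects would also fall on both randomized arms. Nor does the difference between 5.5 and 5.8 show that participants would cross from one limit to the other: it presumes a shared unit, and the size of any shift is not given.

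**Conclusion.** Two points hold.

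- **Unit: certain.** The potassium exclusion is printed a factor of 10 away from the same numeral per litre, and the stopping limit has no volume unit. The practical effect is probably small if staff read both per litre, but that reading is not written down. Creatinine is not involved.
- **Timing: an unresolved conflict.** For participants tapered off antihypertensives, the plan does not establish whether any renal or potassium value exists after withdrawal and before the first dose, and it does not say which sample exclusion (3) uses. If the screening panel is the only one, it is about 1 to 4 weeks old at baseline, assuming a day-0 draw. Participants with no taper are outside this point.

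The size of any clinical effect cannot be derived from the documents. The case for acting is that the rule concerns safety at entry and the repair is cheap.

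**What to change.** 1. State one valid potassium unit, the one the laboratory reports in, in both section 4.2(3) and section 9.
2. Reconcile 6.6, 7.2.1, 7.2.3, 8.2 and Table 2 on whether a BMP is drawn at the baseline visit. If 6.6 and 8.2 mean that visit, mark it in Table 2 and name it in 7.2.3. If they mean the screening panel, say so there. Align the 1-month test in 8.2 with the 2- or 4-week BMP in 7.2.4 in the same edit.
3. State which sample exclusion (3) uses. That choice is for the sponsor and the study physician; no clinical rule is proposed here.

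**Cost.** Items 1 and 3, and item 2 under the screening reading, are wording only. Under the baseline-visit reading, the cost is at most one routine panel per participant on a blood draw that already takes place, so no more than 160 panels at the planned enrollment. If the sponsor names that sample as the governing one, the result would have to be back before randomization, inside the one-week limit off treatment, and some participants could fail screening at that late stage.

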### **8.1 Potential Risks**

The proposed study will utilize widely used and approved procedures including: commonly used neuropsychological questionnaires and interview materials, blood pressure measurements, brain MRI, carotid ultrasound, and blood draws. Neuropsychological assessment may be accompanied by anxiety, frustration and overall fatigue. The attachment and removal of a blood pressure cuff, cuffs for venous occlusion, and ultrasound probe on the neck may cause mild discomfort. Brain imaging requires the participant to stay still and lie down for 50-60 minutes, which may cause boredom and minimal reversible back pain. Because of the closed space and noise, undergoing an MRI may be associated with anxiety or panic reactions. Claustrophobic-prone individuals will not be asked to undergo the MRI portion. We will ask participants to breathe via a mask air richer in CO2 than normal atmospheric air (5-8%) during the brain MRI procedure. The CO2 reactivity procedures were well tolerated by elderly subjects in our prior studies, and have been performed numerous times in our laboratory without complications. The reported potential side effects may include a feeling of dizziness, faintness, or anxiety during CO2 inhalation.

The discontinuation of blood pressure medications may be associated with a risk of marked blood pressure elevation and development of associated neurological or cardiac symptoms: headaches, dizziness, blurred vision, chest pain or ischemic neurological events. In our pilot study, none of the participants experienced these symptoms. To minimize this risk, medications will be slowly tapered over a 2-4 week period while study personnel carefully monitor subjects.

The proposed study will utilize drugs approved by the Food and Drug Administration for the treatment of hypertension. They are well tolerated by young and elderly individuals and have been used extensively in

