receiving coil or conductive materials. Subjects will be screened for magnetic material before each study, per the standard of care at the MRI suite. Patients with pacemakers, aneurysm clips, metallic prostheses or shrapnel fragments are at risk at an MR environment and will be excluded from the neuroimaging portion of the study. Women of childbearing age will not be included. Earplugs or close fitting silicon padded headphones will be provided to protect from damage to the inner ear due to the loud tone produced by the MRI scanner. Subjects will be observed and monitored at all times by the operators, and can be moved out of the machine at their request. Subjects will be able to communicate through an intercom with the physician/scientist or technician at all times. In addition the MR gantry is equipped with a camera allowing continuous monitoring of the subjects from the MR control room; subjects are given a pneumatic bulb that starts off an alarm in the control room in case of emergency. All people entering the exam room where the magnet is located will be screened for magnetic material before entering the room. This will apply to subjects, experimenters, and staff.

(iii) **Incident dementia:** Although limited information is available, it is estimated that the yearly conversion rate is close to 7% in executive MCI. We will screen at each visit for any new diagnosis related to cognition (dementia, delirium, others), new medication started (cholinesterase inhibitors or memantine), or proxy/self-report of new diagnosis of dementia. The physician (PI) will review the clinical history with the study neurologist ([name]) and a consensus diagnosis will be made. We will compare the number of people who develop incident clinical dementia in both groups as part of our safety analyses.

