#### Outcome Analysis

(a) Candesartan and cognitive/neuroimaging outcomes: General linear models will be used to compare the candesartan and lisinopril groups. Our main explanatory variable is the indicator for treatment group. Dependent variables will be the 12-month cognitive and neuroimaging measurements. For the cognitive analyses, our primary outcome is the executive function score derived using item response theory as outlined above in the EXAMINER methodology to account for education, age, and race influences on measures of executive abilities (developed by our collaborator, [name] team). For the cognitive outcome Mixed models with repeated measures (3 measurements) will be used. This procedure allows us to model the covariance structure to account for the potential variability across subjects in times of follow-up visits. Our main explanatory variable is the indicator for treatment group. The test of treatment effects on trial outcomes will be an interaction of treatment by visit (baseline,12 months follow-up). The main covariate adjustments will include history of prior stroke and prior exposure to ACEI/ARB. Additional covariate adjustments will be selected based on baseline statistically significant differences between the 2 randomized groups. The neuroimaging outcomes include measures of global perfusion, reactivity, FA, MD, and tractography metrics described above. **Table 3** provides a list of main variables. The multivariate models of the neuroimaging analysis will include the baseline values of the 12-month outcome variable, randomization stratification variables and other covariates that are significantly differ (at p<0.05) between the 2 groups at baseline. We will assess if the effects of randomized treatment are independent of blood pressure by comparing models with and without blood pressure change from baseline to 12 months. Summary statistics will include the model-adjusted mean and 95% confidence interval for each treatment group, and the mean (95% confidence interval) group difference on each 12-month outcome, as well as a p-value for group differences. All tests of significance on treatment group comparisons will use a two-sided alpha of 0.05.

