## 10.6 Sample Size Estimates

Using ANOVA with repeated correlated measures improves power in clinical trials. The 1 year correlation with baseline repeated measures ranged from 0.3 to 0.5 in our pilot data. The effect size for candesartan relative to lisinopril was 0.48 [mean difference 12 (pooled SD 25 sec)] for TMT-B, 0.41 [mean 5.5(13)] for cerebral blood flow and 0.24 [mean 0.30(1.2)] for vasoreactivity to CO2 in our pilot study. Using a 2-sided  $\alpha = 0.05$ , we estimate that a sample size of 140 will give us 80% power to detect at least 0.24 effect size. To account for dropout rate of 10-15% and a 55% prevalence of eligible subjects, we estimate that we need to screen 332 and enroll 160 to achieve a 140 final sample size.

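### Section 10.6 ties 80% power at N = 140 to the CO2-vasoreactivity effect, but allows only for dropout and not for participants enrolled without MRI or CO2 testing

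*Combined protocol and SAP*

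**What the plan says.** Section 4.2, item (7), sets inability to perform study procedures as an exclusion and then makes two exceptions. The first is that "those with contraindications for MRI will be enrolled but will not undergo the MRI". The second keeps people with lung disease in the trial but out of the CO2 protocol.

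Two later sections widen the unscanned group. Section 8.1: "Claustrophobic-prone individuals will not be asked to undergo the MRI portion". Section 8.2(ii): "Patients with pacemakers, aneurysm clips, metallic prostheses or shrapnel fragments are at risk at an MR environment and will be excluded from the neuroimaging portion".

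Section 10.6 lists three pilot effects, including "0.41 [mean 5.5(13)] for cerebral blood flow" and "0.24 [mean 0.30(1.2)] for vasoreactivity to" CO2. It then makes one statement for the whole trial: "we estimate that a sample size of 140 will give us 80% power to detect at least 0.24 effect size". The Sample Size and Population synopsis and section 10.6 both explain the step from 160 enrolled to 140 final by dropout, put at 10-15%. Neither gives an expected number with MRI or CO2 data, an expected ineligible share, or a way to replace unscanned participants.

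**The concern.** The eligibility rules create three nested groups: everyone enrolled, those who can be scanned, and those who can be scanned and can also breathe CO2. The CO2 challenge takes place during the MRI (section 6.4, Table 1; section 8.1), so vasoreactivity loses people on both counts. The sample-size section has one number for all three groups, and the effect attached to its 80% is the one for the smallest group.

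The analysis cannot recover these people. The imaging models in section 10.5 adjust for the baseline value of the 12-month outcome, and a participant who is never scanned has neither value. The Aim 3A mediation models take imaging variables as outcomes and lose the same people, whereas Aim 3B (cognition) does not. At stake is whether the stated size and power for vasoreactivity are delivered, and whether a reader knows how many people stand behind the imaging results.

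**Working it through.** **Inputs**

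- Section 10.6: 160 enrolled, 140 final, dropout 10-15%, 80% power, effect 0.24. On correlation: "The 1 year correlation with baseline repeated measures ranged from 0.3 to 0.5 in our pilot data".
- Section 10.5: "All tests of significance on treatment group comparisons will use a two-sided alpha of 0.05".
- Section 10.2: 1:1 allocation, so 70 per arm.
- Assumption: a share s of the final 140 has no usable measure, with s from 5% to 30%. The documents give no figure. For vasoreactivity, s combines the MRI and CO2 losses.

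**Step 1: room left by the dropout allowance.** Completers = 160 × (1 − dropout).

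- 10%: 160 × 0.90 = 144, so 4 to spare (4/144 = 2.8%)
- 12.5%: 160 × 0.875 = 140, none to spare
- 15%: 160 × 0.85 = 136, already 4 short

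**Step 2: reproduce the plan's power.** A group-by-time interaction in repeated-measures ANOVA has noncentrality λ = f²·N·m/(1 − ρ). Take f = d/2 = 0.12, m = 2 visits, ρ = 0.5 and N = 140. Then λ = 0.0144 × 140 × 2/0.5 = 8.06 on 1 and 138 degrees of freedom, and power is 80.5%. This matches the claim. Section 10.6 does not state its formula, so this is its apparent basis. (Three visits with ρ = 0.4 give 81.4%.)

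**Step 3: same formula, fewer people.** N = 140 × (1 − s).

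| s (assumed) | N | Power for 0.24 | Effect detectable at 80% |
|---|---|---|---|
| 0% | 140 | 80.5% | 0.238 |
| 5% | 133 | 78.5% | 0.245 |
| 10% | 126 | 76.2% | 0.252 |
| 15% | 119 | 73.8% | 0.259 |
| 20% | 112 | 71.1% | 0.267 |
| 30% | 98 | 65.3% | 0.286 |

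**Step 4: perfusion on the same formula (d = 0.41).** Power is 99.8% at N = 140 and 98.0% at N = 98.

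**Step 5: the model that section 10.5 specifies for imaging.** For a baseline-adjusted comparison (normal approximation), power = Φ(d/√(1 − ρ²) × √(N/4) − 1.96).

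- d = 0.24, N = 140: 31.9% at ρ = 0.3 and 37.4% at ρ = 0.5, before anyone is lost to MRI or CO2 ineligibility.
- d = 0.41, ρ = 0.5: 80.0% at N = 140, 75.7% at 126, 64.9% at 98.

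Step 5 shows a separate and larger problem. In a two-group, two-visit interaction, f = 0.12 corresponds to a difference in change of 4f = 0.48 SD, not 0.24. It matters here because any restated detectable effect has to use the corrected base.

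**The case against.** Several stronger readings are tempting, and the documents do not support them.

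- *Aim 2 cannot reach 140.* That unscanned people count toward the 140 is an inference, though a direct one: they are enrolled, and 140 is the only final number given. No ineligible share is stated, and at 10% dropout about four could be absorbed. A shortfall is very likely, but its size is not established.
- *Power falls below 80% for all imaging outcomes.* On the plan's apparent formula, perfusion does not (step 4). It does under the baseline-adjusted model, but that means replacing the plan's calculation, which is a different point. Section 10.6 gives no planning effect for FA, MD or tractography, so there is no stated DTI power to overstate.
- *The imaging comparison is biased by selection.* Under section 7.2.3 the baseline MRI comes before randomization, and the imaging models adjust for the baseline value. Restriction to people scanned at baseline costs precision and generalizability, not the validity of the randomized contrast.
- *Lung disease narrows all of Aim 2.* It removes people from the CO2 challenge only. In Table 1 of section 6.4 the mask comes off before the perfusion and DTI sequences.
- *Vasoreactivity could drop to 83 people and 58% power.* That takes 140 × 0.70 × 0.85 and so stacks two upper limits that have no source in the documents.

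It can also be said that the required 95% confidence intervals will show the precision achieved, that enrolling people who cannot be scanned protects the primary outcome's sample, and that the base calculation is the bigger fault. All three are fair. None of them supplies the missing denominator for the outcome whose effect size the power claim uses.

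**Conclusion.** The point holds as a gap in the sample-size statement for secondary outcomes. Section 10.6 attaches 80% power at N = 140 to the vasoreactivity effect, while other sections enroll people who cannot provide that measure and the only allowance is for dropout. Unless ineligibility is almost nil, vasoreactivity, the other MRI outcomes and Aim 3A will have fewer than 140.

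On an assumed 5-30% without the measure, the loss for 0.24 on the plan's apparent formula is about 2 to 15 percentage points. That range is illustrative. EXAMINER needs no MRI and is unaffected. The fix is cheap and worth making, but this is not a flaw in the primary comparison.

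**What to change.** - In section 10.6, keep 140 for EXAMINER only. State the expected number of MRI-capable completers and, separately, of completers who are both MRI- and CO2-capable, with the assumed shares shown.
- Restate the detectable effect for each imaging outcome on those numbers, using the baseline-adjusted model of section 10.5 and not the calculation behind the present 0.24.
- In sections 3 and 10.4, define the Aim 2 and Aim 3A analysis set as randomized participants recorded as MRI-capable before randomization. Add CO2 capability for vasoreactivity only.
- Reconcile the two CO2 rules before estimating that loss. Section 4.2(7) refers to a history of asthma, COPD or other significant lung disease; section 8.2(i) refers to active asthma or COPD.

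The cost is wording, plus a less favorable stated sensitivity for the imaging outcomes. Who is enrolled does not change. For comparison, securing 140 people with the measure at 12.5% dropout would need 160/(1 − s) enrolled: 169 at s = 5% and 229 at s = 30%.
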